8.3.4. Regulatory Reporting Requirements for SAEs

Prompt notification by the investigator to the sponsor of an SAE is essential so that legal obligations and ethical responsibilities regarding the safety of the study treatment under clinical investigation are met.

The sponsor has a legal responsibility to notify both the local regulatory authority and other regulatory agencies about the safety of the study treatment under clinical investigation. The sponsor will comply with country-specific regulatory requirements regarding safety reporting to regulatory authorities, IRBs/IECs, and investigators.

Investigator safety reports must be prepared for suspected unexpected serious adverse reactions (SUSARs) according to local regulatory requirements and sponsor policy, and forwarded to investigators as necessary.

An investigator who receives an investigator safety report describing an SAE or other specific safety information (ie, summary or listing of SAEs) from the sponsor will review and then file it with the Investigators Brochure, and will notify the IRB/IEC, if appropriate according to local requirements.

8.3.5. Pregnancy

All subject pregnancies that are identified during or after this study, where the estimated date of conception is determined to have occurred during study drug therapy or within 28 days of the last study treatment need to be reported, followed to conclusion, and the outcome reported, even if the subject is discontinued from the study. The investigator should report all pregnancies within 24 hours using the Pregnancy Form. Monitoring of the pregnancy should continue with 1 or more Pregnancy Form(s) detailing progress, and a Two-Month Follow-up Pregnancy Report Form detailing the outcome, should be submitted.

Pregnancy itself is not regarded as an AE unless there is suspicion that the investigational product under study may have interfered with the effectiveness of a contraceptive medication. Likewise, elective abortions without complications are not considered AEs. Any SAEs associated with pregnancy (eg, congenital abnormalities/birth defects, or any other serious events) must additionally be reported as such using the Serious Adverse Event (SAE)/Reportable Event Form (see Section 10.3). Spontaneous miscarriages should also be reported and handled as SAEs.

Subjects will be instructed to immediately notify the investigator of any pregnancies.

A subject who becomes pregnant must immediately be discontinued from study treatment and withdrawn from the study.

Attempts to obtain the pregnancy follow-up and pregnancy outcome information detailed above are necessary even if a subject discontinues treatment and withdraws from the study because of pregnancy.

8.3.6. AEs/SAEs Experienced by Nonsubjects Exposed to Study Treatment

Nonsubjects are persons who are not enrolled in the study but have been exposed to study treatment, including instances of diversion of study treatment. All such AEs/SAEs occurring in nonsubjects from such exposure will be reported to Endo (when the nonsubject agrees) on the Serious Adverse Event (SAE)/Reportable Event Form regardless of whether the event is serious or not. Instructions for completing the form for events experienced by nonsubjects will be provided. SAEs occurring in nonsubjects exposed to study medication will be processed within the same SAE reporting timelines as described in Section 10.3. Additionally, the drug accountability source documentation at the site should reflect this occurrence.

8.3.7. Adverse Events of Special Interest

AESIs for this study include:

- Bruising, ecchymosis, hematomas, and contusions that occur remote to the site of drug administration.
- Any hypersensitivity reactions.
- Local AEs associated with the injection site, including bruising, pain, nodules/mass, ulceration, erythema, pruritus, swelling, and/or induration.

These events will be reported as AEs in the eCRF. All AEs will be evaluated for seriousness and severity. If any of these events meet the criteria for an SAE, they will also be reported as such using the procedure outlined in Section 10.3.

8.4. Treatment Overdose

Study treatment overdose is any accidental or intentional use of treatment in an amount higher than the dose indicated by the protocol for that subject. Study treatment compliance should be reviewed to detect potential instances of overdose (intentional or accidental).

Any treatment overdose during the study should be noted on the study medication eCRF.

An overdose is not an AE per se, however all AEs associated with an overdose should both be entered on the Adverse Event eCRF and reported using the procedures detailed in Section 10.3, even if the events do not meet seriousness criteria. If the AE associated with an overdose does not meet seriousness criteria, it must still be reported using the Endo Serious Adverse Event (SAE)/Reportable Event Form and in an expedited manner, but should be noted as nonserious on the form and the Adverse Event eCRF.

8.5. Pharmacokinetics

Not applicable.

8.6. Pharmacodynamics

Prior to the first MRI and biopsy, the investigator will select 3 dimples from the 2 treatment areas (both buttocks or both thighs) for MRI and biopsy evaluation from the 4 well-defined, isolated dimples that are considered moderate or deep in depth identified at screening (see Section 5.1, Item 5). The 3 selected dimples should be distributed across both regions of the treatment area (eg, 1 dimple on the left thigh [or buttock] and 2 dimples on the right thigh [or buttock], or vice versa). The investigator or designee will mark and label these 3 dimples in a manner that will allow them to be relocated for subsequent MRIs and biopsies (see the Clinical Operations Study Manual for specific instructions). To ensure proper healing, the dimple biopsied at screening (Dimple 1) will not receive treatment with CCH. Dimple 2 and Dimple 3 will receive the entire CCH treatment course in this study.

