^a Performed prior to any study-required assessments, unless exceptions granted for standard of care procedures. A separate informed consent may be used for HIV testing and must be signed before the sample is collected, if required.

^b Should be reassessed and verified prior to dosing.

^c Vital signs will be collected up to 4 hours prior to, and at 15 and 30 minutes after, study treatment administration on Days 1, 22, and 43.

^d Urine pregnancy test should be completed prior to the MRI.

^e At screening all 4 potential treatment areas (each buttock and each thigh) will be imaged; and CR-PCSS, PR-PCSS, and Hexsel CSS assessments will be done for each potential treatment area (each buttock and each thigh).

^f Before and after marking dimples for treatment. No manipulation of the treatment area should be done prior to the “before” photographs.

^g Screening MRIs will be performed after all other screening assessments (except the biopsy) have been completed. MRIs may be repeated within the screening window as often as necessary to obtain evaluable images.

^h The Day 71 and Day 251 MRIs may be performed up to 7 days prior to the indicated visit. The MRI must be completed before the biopsy required for these visits. The Day 251/Early Termination MRI is not required for subjects who withdraw from the study (early termination). The Day 71 and Day 251 MRIs may be repeated as often as necessary to obtain an evaluable image.

Table 1: Schedule of Activities (Continued)

ⁱ The screening biopsy will be performed after all other screening assessments (including MRI) are completed. The screening biopsy will be performed at least 14 days prior to the Day 1 Treatment Visit. The investigator must examine and confirm sufficient healing of the biopsy site before dosing on Day 1. The timing of all subsequent visits will be based on the actual date that the first dose of CCH is administered.

^j The Day 71 and Day 251 imaging for efficacy, PR-PCSS, and CR-PCSS must be completed prior to the biopsy sample collection required at those visits. The Day 251/Early Termination biopsy is not required for subjects who withdraw from the study (early termination). For subjects who received less than 3 doses of CCH prior to 18 March 2020, no Day 71 or Day 251 biopsy samples will be collected.

^k Visit not required for subjects who had less than 3 doses of CCH prior to 18 March 2020.

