5. SELECTION AND WITHDRAWAL OF SUBJECTS

5.1. Subject Inclusion Criteria

In order to be eligible to participate in the study, at the Screening Visit and on Study Day 1, subjects must:

1. Be female and ≥ 18 and ≤ 50 years of age at the time of consent.

2. Have both buttocks or both posterolateral thighs with:
 - a. A score of 3 or 4 (moderate or severe) as reported by the investigator using the CR-PCSS.
 - b. A Hexsel CSS total score of ≤ 13 .
 - c. A Hexsel CSS Subsection A “Number of Evident Depressions” score of > 0 .
 - d. A Hexsel CSS Subsection B “Depth of Depressions” score of 2 (medium depth depressions) or 3 (deep depressions).
3. Have a body mass index (BMI) score between 18.5 kg/m² to 29.9 kg/m² and intends to maintain stable body weight throughout the duration of the study (from the Screening Visit through the Day 251/Early Termination Visit). A variation of $\leq 10\%$ from the Day 1 Visit weight is permitted.
4. Be willing and consent to undergo human immunodeficiency virus (HIV) and hepatitis B testing, as well as double punch biopsy and MRI procedures.
5. Have a minimum of 2 well defined and isolated cellulite dimples that are considered moderate or deep in depth in each treatment area (each thigh or each buttock, for a total of 4 such dimples), of which 3 (Dimples 1, 2 and 3) will be selected for MRI and biopsy procedures.
6. Be willing to apply sunscreen to the treatment area before each exposure to the sun for the duration of the study (from the Screening Visit through the Day 251/Early Termination Visit).
7. Be judged by the investigator to be in good health, based upon the results of a medical history, physical examination, electrocardiogram (ECG), and laboratory profile at screening.

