8.6.2. Double Punch Biopsy

Subjects will have a total of three 8 mm double punch biopsies done, 1 in each of the 3 dimples selected for MRI and biopsy (Dimples 1, 2, and 3) at the times outlined in the Schedule of Activities (Section 1.2). Detailed directions of the collection, processing, storage, handling and shipment of the biopsy samples will be provided in the Clinical Operations Study Manual. The investigator must examine and confirm sufficient healing of the biopsy site before dosing on Day 1.

Subjects who received all 3 doses of study drug prior to 18 March 2020 will have Day 71 and 251 biopsies, if willing to do so. Subjects who received less than 3 doses of study drug prior to 18 March 2020 will not have the Day 71 and Day 251 biopsies performed.

De-identified biopsy samples may be stored for a maximum of 5 years (or according to local regulations) following the last sample collection from the last subject last visit for the study at a facility selected by the sponsor to enable further analysis including to develop methods, assays, prognostics and/or companion diagnostics related to specify the intervention target, disease process, pathways associated with disease state, and/or mechanism of action of the study intervention.

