3.14.2. Double Punch Biopsy

Biopsies will be performed at Screening, Day 71 and Day 251. The Screening biopsy will be performed on Dimple 1 after all other screening assessments, including MRI, are completed. The Screening biopsy will be performed at least 14 days prior to the Day 1 Visit.

The Day 71 biopsy will be performed on Dimple 2 and the Day 251 biopsy will be performed on Dimple 3 after completion of imaging for efficacy, PR-PCSS, and CR-PCSS at Day 71 and Day 251 respectively.

The Day 251/Early Termination biopsy is not required for subjects who withdraw from the study (early termination).

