4.5.5. Proportion of Subjects with No Change (or Worsening) from Baseline (Tertiary Endpoints)

Complete loss of Response at Days 161 and 251 is defined as worsening of cellulite severity improvement on PR-PCSS/CR-PCSS /Hexsel CSS total score ratings at Days 161 and 251 compared to the score at Day 71, where cellulite severity returns to baseline levels or worse.

Tertiary endpoints will be analyzed for each scale separately.

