7.6. Efficacy Analyses

Efficacy parameters will be summarized by treatment area (left or right) and treatment region (buttock or thigh) using the Evaluable Population.

PR-PCSS, CR-PCSS and Hexsel CSS total score ratings and the level of change from baseline will be summarized as per below sections.

A listing for digital photography will be provided with date and time for photos taken and reasons for photos not taken per protocol.

Individual listings will be provided for PR-PCSS ratings, CR-PCSS ratings and Hexsel CSS ratings and total scores.

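### The Day 71 biopsy of treated Dimple 2 may confound the Day 161 and Day 251 durability ratings on that side, and the planned left/right summaries do not show which side was biopsied

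*Protocol*

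**What the plan says.** **Biopsies.** Protocol 8.6.2: "Subjects will have a total of three 8 mm double punch biopsies done", one in each selected dimple. Dimple 1 is biopsied at screening and never treated. Dimples 2 and 3 are treated at all three sessions. For the later specimens, SAP 3.14.2 states: "The Day 71 biopsy will be performed on Dimple 2 and the Day 251 biopsy will be performed on Dimple 3".

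**Placement.** Protocol 8.6: "The 3 selected dimples should be distributed across both regions of the treatment area", with the example "1 dimple on the left thigh [or buttock] and 2 dimples on the right thigh [or buttock], or vice versa". Neither sentence ties a dimple number to a side. Inclusion item 5 supplies the candidates: "Have a minimum of 2 well defined and isolated cellulite dimples that are considered moderate or deep in depth in each treatment area".

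**Order of events.** The baseline ratings precede the Dimple 1 biopsy, since in the Protocol Schedule of Activities "The screening biopsy will be performed after all other screening assessments (including MRI) are completed". At Days 71 and 251, footnote j puts photography, PR-PCSS and CR-PCSS before the biopsy. It does not name Hexsel CSS.

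**Durability endpoint.** Protocol section 3 counts subjects who are unchanged or worse than baseline at Days 161 and 251 on PR-PCSS, CR-PCSS and Hexsel CSS. SAP 4.5.5 adds a comparison with Day 71, and complete loss is a worsening "where cellulite severity returns to baseline levels or worse".

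**Analysis.** SAP 7.6: "Efficacy parameters will be summarized by treatment area (left or right) and treatment region (buttock or thigh) using the Evaluable Population". SAP 7.6.3 adds only counts and percentages. Neither document classifies sides by biopsy status or tells raters how to treat a biopsy site.

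**The concern.** The scales rate the whole buttock or thigh, so a biopsy site is part of what is scored. On the Dimple 2 side, the Day 161 and Day 251 ratings reflect both the durability of CCH and the after-effects of removing tissue from a treated dimple. Protocol 2.3 names permanent scarring and damage to structures beneath the skin as biopsy risks. A residual depression could be scored as relapse. Removal of the dimple could be scored as lasting benefit.

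The scales are coarse enough for one site to matter in some subjects. In SAP Table 6 the Hexsel depression count changes grade between 4 and 5 and between 9 and 10, so one depression more or fewer can move the total by a point. For a subject who had improved by a single step, that decides whether she counts as a complete loss.

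Left/right columns do not help, because Dimple 2 may be on the left in one subject and on the right in another.

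**Working it through.** The plan gives no figure on this point to reproduce. The check is a count of the arrangements that the placement rule allows.

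**1. Timing.** The Day 71 biopsy nominally precedes the durability ratings by 161 − 71 = 90 days and 251 − 71 = 180 days.

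**2. Arrangements.** Three labelled dimples on two sides, with both sides used, give 2³ − 2 = 6 labellings. These are three patterns, each with a mirror image:

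| Pattern | Dimple 2 side, biopsies before the Day 251 biopsy | Other side, biopsies before the Day 251 biopsy |
|---|---|---|
| 1 and 2 together, 3 alone | screening and Day 71 | none |
| 1 and 3 together, 2 alone | Day 71 | screening |
| 2 and 3 together, 1 alone | Day 71 | screening |

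**3. Sides without the Day 71 biopsy.** In every pattern there is exactly one per subject, so 12 of the 24 rated sides in 12 subjects, whatever the labelling.

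**4. Sides with no study biopsy through the Day 251 PR-PCSS and CR-PCSS.** Such a side exists only in the first pattern: 2 of 6 labellings, or 1/3. Ordered choices of 3 dimples from 4 (2 per side) give the same answer: 8 of 24 leave such a side and 16 of 24 do not.

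**5. Expected numbers.** If labels fall at random (assumption), 12 × 1/3 = 4 subjects keep a side with no biopsy and 12 × 2/3 = 8 do not. The investigator selects and labels the dimples, so the true number lacking one can be anything from 0 to 12. Let p be the probability that a subject lacks such a side. Then P(at least 7 of 12) = Σ C(12,k) pᵏ(1−p)¹²⁻ᵏ for k = 7 to 12:

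| p | Expected number lacking | P(at least 7 of 12) |
|---|---|---|
| 0.50 | 6 | 0.39 |
| 2/3 | 8 | 0.82 |
| 0.75 | 9 | 0.95 |

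**6. What one misclassified subject does.** With the planned balance there are about 12/2 = 6 subjects per region. One subject then moves a region-by-side percentage by 1/6, about 17 points.

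**7. The side without the Day 71 biopsy.** In two of the three patterns it holds Dimple 1. That site already existed at the Day 71 rating, so no new biopsy intervenes between Day 71 and Days 161 and 251. It did not exist at the baseline rating, so the comparison with baseline still carries it. Hence the need to flag it.

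**The case against.** **No effect is shown.** PR-PCSS and CR-PCSS are five-level ratings of a whole area, with up to 12 injections per area per session. No section shows that one 8 mm site shifts such a rating, or in which direction. Scarring is listed as a risk, not an expected result. Subjects with abnormal wound healing, keloids or hypertrophied scars are excluded, and biopsy sites are examined at Day 85. This stands: the bias is possible, and its size and sign are unknown.

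**The sides can be compared.** A reader might infer that loss of effect cannot be told from biopsy scar at all. The documents do not support that. Left and right are rated separately, individual ratings are listed, and one side always escapes the Day 71 biopsy. A partial check is possible; it is simply not planned.

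**The number is an assumption.** A reader might also infer that most subjects have no unbiopsied side. That follows only if labels are random and the screening biopsy is counted as well. Protocol 8.6 refers marking and labelling instructions to the Clinical Operations Study Manual, which is not among the documents.

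**Biopsies may stop.** Protocol 9.4 ends further biopsies if the interim analysis identifies no changes. That would spare later subjects only, because the interim follows at least 4 subjects completing Day 71.

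**The endpoint is tertiary.** The study is open-label, uncontrolled and descriptive, its sample size rests on histology, and the Day 71 biopsy serves a secondary endpoint. This also stands. It argues for a change in reporting first, and against insisting on a new biopsy layout.

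**Conclusion.** The concern holds in limited form. The Day 71 biopsy falls between the Day 71 reference rating and both durability ratings of the same whole side, so the Dimple 2 side may be confounded at Days 161 and 251. The planned left/right summaries do not separate that side from the other.

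In subjects biopsied as scheduled, half of the rated sides (12 of 24) carry the Day 71 biopsy and half do not. Protocol 8.6 does not guarantee a side free of any study biopsy. About 8 of 12 subjects would lack one under random labelling, within a permitted range of 0 to 12. Neither figure measures bias in the ratings, which the documents do not allow anyone to estimate.

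Priority is modest: this is a cheap improvement to a tertiary, descriptive endpoint.

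**What to change.** **Main change, SAP 7.6.3.** Summarise the Day 161 and Day 251 PR-PCSS, CR-PCSS and Hexsel endpoints by biopsy status of the side: the Dimple 2 side against the side without the Day 71 biopsy, flagging whether Dimple 1 lies on the latter. Read the side without the Day 71 biopsy first for durability. Classify by biopsies actually taken, so that subjects whose Day 71 biopsy is not done are placed correctly.

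**Footnote j (Protocol and SAP schedules) and SAP 3.14.2.** Add Hexsel CSS to the assessments required before the Day 71 and Day 251 biopsies. Otherwise the order is not fixed for one of the three scales.

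**Optional, subjects not yet labelled.** Protocol 8.6 and SAP 3.14 could place Dimples 1 and 2 on one side and Dimple 3 on the other. The present rule already permits this, and inclusion item 5 makes it feasible. Each retained subject would then have a side unbiopsied through the Day 251 ratings, given the Hexsel change.

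**Cost.** The main change needs one classification variable and no new procedure or subject. The documents do not say that the side of each dimple is an eCRF field, so it may have to be taken from labelling records or photographs. Cells are small: about 6 sides per region and status. With the Dimple 1 flag and random labels, the sides without the Day 71 biopsy split into about 6 × 1/3 = 2 and 6 × 2/3 = 4 per region, so a listing would serve better than percentages there.

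The optional layout costs more. The Day 251 specimen would always come from the side opposite the screening and Day 71 specimens, tying side to visit in the histology comparison. The biopsied side would also always hold untreated Dimple 1, so the contrast between sides would not isolate the biopsy effect. For these reasons it is secondary.

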8.6.1. MRI

MRIs of each of the 3 dimples selected for MRI and biopsy (Dimples 1, 2, and 3) will be performed on all subjects at times outlined in the Schedule of Activities (Section 1.2). Screening, Day 71, and Day 251 MRIs may be repeated as often as necessary to obtain an evaluable image. Repeat screening MRIs must take place within the screening window. MRIs must be completed prior to the required biopsies. Specific instructions for the MRI procedures will be provided in the Clinical Operations Study Manual.

All MRIs from this study are the property of Endo and de-identified images may be utilized for clinical development, scientific communication, marketing, regulatory purposes, and/or legal applications as required/desired by Endo.

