9. STATISTICAL CONSIDERATIONS AND METHODS

9.1. Sample Size Determination

There was no formal sample size calculation for this study. A total of 12 subjects is considered sufficient to determine if biopsy will demonstrate changes in histopathology associated with CCH treatment while exposing the minimum number of subjects possible to the risks associated with this invasive procedure.

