9.3.2. MRI and Biopsy Analyses

A descriptive summary of changes from baseline seen in MRI and biopsy results will be provided for the Evaluable Population.

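### Histology change from baseline compares an untreated dimple with treated ones; with no stated label rule or masked reading, labelling habit or reader expectation could mimic or hide a CCH effect

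*Protocol*

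**What the plan says.** Protocol 8.6 has the investigator choose three of the four qualifying dimples, with both sides of the body represented. On labelling it says: "The investigator or designee will mark and label these 3 dimples in a manner that will allow them to be relocated". For how to do this it refers the site to a manual: "see the Clinical Operations Study Manual for specific instructions". It gives healing as the reason that "the dimple biopsied at screening (Dimple 1) will not receive treatment with CCH"; Dimples 2 and 3 receive the full course.

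The Schedule of Activities and SAP 3.14.2 place the screening biopsy in Dimple 1, the Day 71 biopsy in Dimple 2 and the Day 251 biopsy in Dimple 3. For the analysis, Protocol 9.3.2 states: "A descriptive summary of changes from baseline seen in MRI and biopsy results will be provided". SAP 4.7.2 compares screening histopathology with the Day 71 and Day 251 samples.

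Protocol 6.5 and SAP 3.7 set aside treatment blinding and randomization because the study is open-label with no randomization. Neither document says whether slides or images are read with visit, dimple or dosing status concealed.

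**The concern.** No dimple is biopsied twice, so every histology change is a difference between two dimples of the same subject, one untreated and one treated. If the site tends to give label 1 to the shallowest (or deepest) dimple, and depth is related to what the pathologist measures, a difference appears without any drug effect, or a real one is cancelled. Such a habit needs no bad faith: Protocol 6.3 says treatment aims at the appearance of the whole area, so leaving the least prominent dimple untreated would be a natural choice. Separately, a reader who knows which sample is post-treatment may see what is expected.

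Histology is a secondary endpoint at Day 71 and a tertiary one at Day 251. It also appears in the rationale for the sample size: "A total of 12 subjects is considered sufficient to determine if biopsy will demonstrate changes in histopathology associated with CCH treatment". Under Protocol 9.4 it contributes to deciding whether further MRIs and biopsies are done, possibly on as few as 4 newly dosed subjects and with no threshold set.

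**Working it through.** **Step 1. Which dimple is observed when** (Schedule of Activities; SAP 3.14.1 and 3.14.2).

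| | Screening | Day 71 | Day 251 |
|---|---|---|---|
| Biopsy | 1 | 2 | 3 |
| MRI | 1, 2, 3 | 2, 3 | 3 |

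Histology has no same-dimple baseline. MRI has one for Dimples 2 and 3, so labelling does not bias the same-dimple MRI comparison. Reading with knowledge of the visit could affect both.

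**Step 2. Is there a plan figure to reproduce?** No. Protocol 9.1 says there was no formal sample size calculation. The documents give no histology variable, no between-dimple variance and no correlation between depth and histology.

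**Step 3. Illustrative model; every input is an assumption.**
- Visible depth of the three dimples: independent standard Normal.
- Histology H = ρ × depth + √(1 − ρ²) × noise, with SD 1 and no drug effect. ρ is taken as 0.3 and 0.5.
- In a share q of subjects (0.25 and 0.50) Dimple 1 is the depth extreme, always in the same direction, and Dimple 2 is one of the other two at random. Otherwise labels are random.

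**Step 4. Spurious mean shift, Dimple 2 minus Dimple 1.** The expected extreme of three standard Normals is 3/(2√π) = 0.846 from the mean. The other two average half that on the opposite side. The gap is 1.5 × 0.846 = 1.269, so shift = q × ρ × 1.269.
- ρ = 0.3: 0.25 × 0.3 × 1.269 = 0.10; 0.50 × 0.3 × 1.269 = 0.19.
- ρ = 0.5: 0.25 × 0.5 × 1.269 = 0.16; 0.50 × 0.5 × 1.269 = 0.32.

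**Step 5. Chance of a consistent-looking pattern.** Let p be the simulated probability that one subject shifts in the favoured direction. Protocol 9.4 names no direction, so both are counted: p⁴ + (1 − p)⁴ for 4 of 4, and the two binomial tails for at least 10 of 12.

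| ρ | q | p | 4 of 4, either way | ≥10 of 12, either way |
|---|---|---|---|---|
| random labels or ρ = 0 | – | 0.500 | 12.5% | 3.9% |
| 0.3 | 0.25 | 0.527 | 12.7% | 4.2% |
| 0.3 | 0.50 | 0.554 | 13.4% | 5.2% |
| 0.5 | 0.25 | 0.546 | 13.1% | 4.8% |
| 0.5 | 0.50 | 0.593 | 15.1% | 8.0% |

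Example: 0.593⁴ + 0.407⁴ = 0.1237 + 0.0274 = 0.151.

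**Step 6. Where the truth may lie.** The candidates are already "isolated dimples that are considered moderate or deep in depth identified at screening". That narrows the spread in depth and points to the lower figures. Conversely, a habit followed in every subject (q = 1) would give shifts of 0.38 and 0.63 SD and 4-of-4 chances of about 16% and 23%; nothing in the documents supports so uniform a habit.

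The effect of reader expectation is not quantified, because the documents give no basis for a figure. Random labels would not remove it.

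**The case against.** The strongest case is that this is a small descriptive mechanism study whose primary endpoint is PR-PCSS. The between-dimple design is open and has a stated reason, and no histology test is planned. All three dimples must have evaluable screening MRIs, so baseline imbalance visible on MRI can be examined. Random labels and masking would leave time and injection effects in place. All of this stands and limits the weight of the point.

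Several stronger readings are tempting, but the documents do not support them:
- *That labelling is biased or reading is unmasked.* The documents are silent, which is different. A label rule or masked reading may be in the Clinical Operations Study Manual or in separate imaging or pathology instructions, none of which is supplied. The manual's stated scope is MRI procedures ("Specific instructions for the MRI procedures will be provided in the Clinical Operations Study Manual") and sample logistics ("Detailed directions of the collection, processing, storage, handling and shipment of the biopsy samples will be provided in the Clinical Operations Study Manual"). That neither shows nor excludes a reading rule.
- *That the interim risk could double.* Counting one direction only, 4 of 4 goes from 6.3% to as much as 12.3%. The interim question has no direction, so the table above applies.
- *That the sample of 12 rests on histology alone.* The same sentence in Protocol 9.1 also cites keeping biopsy exposure to a minimum.
- *That a hidden histology effect would by itself end the biopsies.* Protocol 9.4 asks about morphology and/or histology, so it would contribute to stopping only if MRI also showed no change. A spurious histology signal could, however, support continuing.

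**Conclusion.** The point holds as a design weakness of optional to moderate weight. The histology comparison is between an untreated and a treated dimple, no allocation rule for the labels is stated, and no masked reading is stated. Under the assumed values the spurious shift is 0.10 to 0.32 between-dimple SD. The chance that all 4 interim subjects move the same way rises by 0.2 to 2.6 percentage points, and for at least 10 of 12 by 0.3 to 4.1 points. These figures depend on an assumed q and ρ, Normal independent depths and a habit that runs in one direction. The reader effect is additional and of unknown size. The case for acting is that the remedy is inexpensive and cannot be applied to labels once a subject has been screened.

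**What to change.** Check the Clinical Operations Study Manual and any imaging or pathology instructions first. If they already set a label rule or masked reading, state it in the protocol. Otherwise:

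- **Protocol 8.6, newly screened subjects:** once the three dimples are chosen under the existing left/right rule, assign labels 1, 2 and 3 at random, by IRT or a prepared list. The rule concerns the set of three, so all 6 label orders satisfy it. Dimple 1 still stays untreated.
- **Protocol 8.6.1 and 8.6.2:** have the planned readers assess coded slides and single-dimple images in random order, without visit, dimple number or dosing status, reading screening and Day 71 material together. The check that an MRI is evaluable can stay unmasked.
- **SAP 4.7.2 and 7.8.2:** describe histology as a within-subject, between-dimple comparison, and tabulate the screening MRI findings of Dimples 1, 2 and 3 side by side.

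The cost is one assignment step, coding of slides, splitting of MRI sets by dimple, and one table; no biopsy or visit is added. Re-reading earlier material with Day 251 is optional. For 12 subjects it would mean up to 12 × 2 = 24 earlier biopsies and 24 earlier Dimple 3 images, which is more than this endpoint needs.

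The downside is that the investigator no longer chooses which selected dimple stays untreated. Masking may also be incomplete where treated tissue is recognisable. Elapsed time, injection effects and chance imbalance between dimples remain, because no untreated dimple is biopsied after treatment.
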